## **Study Protocol:**

**Study Design:** The effectiveness-implementation hybrid design of this proposal enables the simultaneous evaluation of both effectiveness outcome measures as well as of the process of implementation. We propose a type 2 hybrid trial to test both the effectiveness of the clinical intervention (the 5A's delivered via a CTTS) while simultaneously gathering multi-level contextual data regarding potential barriers and facilitators to clinical implementation. Effectiveness questions will be explored using a two-armed cluster randomized controlled design. Implementation questions include: (1) what are the facilitators/barriers to delivering tobacco treatment to pregnant women using existing healthcare provider in the clinic settings; (2) how likely is intervention delivered as prescribed (fidelity); (3) what implementation strategies might maximize the facilitators and overcome barriers to implementation; and (4) what potential modifications could be made to maximize implementation? This pilot project will gather quantitative and qualitative data for a mixed-method, multi- stakeholder process evaluation of intervention training and delivery among 12 clinic staff and providers involved in the project. Furthermore, our use of Medicaid claims data will enhance understanding of the strengths and limitations of these data for future evaluations.

**Aim 1 - Effectiveness evaluation:** As part of routine standard of care, all pregnant Medicaid patients who receive first trimester screening through the intervention or Tobacco Treatment as Usual (TTAU) clinic will also be asked about their tobacco use consistent with the ACOG recommended questionnaire (the standard of care for TTAU is the ACOG recommended questionnaire in Box 1. ACOG 5A's). All women who report tobacco use would be considered eligible to participate to receive ToPIC or TTAU. Participants in the intervention and TTAU clinics will be informed their urine will be tested for cotinine to confirm tobacco use at each data collection point and be informed of their results in compliance with ACOG clinical standards. Inclusion criteria are: 1. Pregnant and age 18-44; 2. Tobacco user (self-reported) 3. Can read and write in English; and 4. Medicaid subscriber.

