### **BOX 1. ACOG's 5A's**

1. **ASK** the patient about smoking status at the 1st prenatal visit and follow-up with her at subsequent visits.
  - A. I have never smoked or I have smoked fewer than 100 cigarettes in my lifetime
  - B. I stopped smoking before I found out I was pregnant and I am not smoking now
  - C. I stopped smoking after I found out I was pregnant, but I am not smoking now
  - D. I smoke now, but I cut down on the number of cigarettes I smoke since I found out I was pregnant
  - E. I smoke regularly now, about the same as before I found out I was pregnant
2. **ADVISE** the patient who smokes to stop by providing advice to quit with information about the risks of continued smoking to the woman, fetus, and newborn.
3. **ASSESS** the patient's willingness to attempt to quit smoking at the time. Quitting advice, assessment, and motivational assistance should be offered at subsequent visits.
4. **ASSIST** the patient willing to make an attempt using counseling and pharmacotherapy to help her quit.
5. **ARRANGE** the follow-up contact, in person or by telephone, preferably within the first week after the quit date.

Usual Care (TTAU): Eligible women randomized to the control group will be informed of the risks of tobacco use and benefits of quitting using the ACOG 5A's approach by their healthcare provider. This standard takes approximately 5-15 minutes, and is offered at each prenatal and postpartum appointment. The research nurse or key personnel will invite participants to complete the tobacco use questionnaires (TUQ), urine cotinine validation, and Expired Air Carbon Monoxide (EACO) analysis to assess ongoing tobacco use at the designated time points; participants will receive a monetary gift card as compensation for their time, at the denominations listed below in Table 1.

The Intervention (ToPIC): Eligible women randomized to the intervention will receive TTAU plus ToPIC administered by the CTTS. At least once monthly, at routinely scheduled prenatal visits or through telephone, the CTTS will provide cessation counseling (see components of a typical counseling session in Box 2). The CTTS will invite participants to complete TUQs, urine cotinine validation and EACO analysis to assess ongoing tobacco use at the designated time points; participants will receive a monetary gift card as compensation for their time. See summary of study procedures in Table 1.

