**Table 1. Summary of Study Procedures**

Time points	ToPIC participants	TTAU participants	Outcome	Compensation
Pregnant Patient Participants:				
Baseline <20 weeks gestation	
 
• Urine cotinine
 
• EACO
 
• ACOG tobacco use screen
 
	
 
• Urine cotinine
 
• EACO
 
• ACOG tobacco use
 
	Eligibility screen for tobacco	\$10
Monthly through end of pregnancy at regularly scheduled prenatal visits	
 
• CTTS tobacco treatment education support, including
 
• Individualized treatment plan (baseline)
 
• 5As
 
• Motivational Interviewing
 
• Navigation to resources
 
	
 
• 5As, as per usual
 
		
28-34 weeks gestation	
 
• Urine cotinine
 
• EACO
 
• TUQ
 
	
 
• Urine cotinine
 
• EACO
 
• TUQ
 
	Tobacco cessation or reduction	\$10
Postpartum 2-8 weeks after delivery	
 
• Urine cotinine
 
• EACO
 
• TUQ
 
	
 
• Urine cotinine
 
• EACO
 
• TUQ
 
	Tobacco cessation or reduction	\$20
Postpartum 12-18 weeks after delivery	
 
• Urine cotinine
 
• EACO
 
• TUQ
 
	
 
• Urine cotinine
 
• EACO
 
• TUQ
 
	Tobacco cessation or reduction	\$20

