### Statistical Analysis Plan

Analysis and estimated power: **Primary outcome:** The primary outcome is smoking cessation in the third trimester, defined as urine cotinine level of <100 ng/mL. **Secondary outcomes** include: self-reported number of cigarettes smoked/day, smoking cessation after delivery, infant birth weight, gestational age at delivery, health care utilization outside of scheduled normal prenatal and infant well-child visits. Two-factor mixed models with group by time interactions will be employed to analyze longitudinal continuous data collected over the course of the trial. Significant main and interaction effects will be explored further using Tukey post-hoc tests. Generalized estimating equation (GEE) modeling will be used to test for significant differences between groups and across time for categorical and dichotomous outcomes; these models will also consider possible group by time interactions. Post-hoc analysis of significant main or interaction effects in the GEE models will be accomplished using contrasts. Demographic and personal factors (e.g., maternal age, gestational age at enrollment) may be included as covariates if linked to outcomes in bivariate analysis. We **hypothesize** that compared with the TTAU group, the ToPIC group will have higher tobacco cessation rates, fewer infants born preterm, and fewer ill child health care visits. While we will assess group differences over time

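### The entry window differs between Aim 1, Table 1 and the inclusion criteria, and gestational age at enrollment is adjusted for only if a bivariate screen selects it

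*Combined protocol and SAP*

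**What the plan says.** Three places bear on when a woman may enter.

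- **Study Protocol, Aim 1.** The ACOG tobacco questionnaire is put to "all pregnant Medicaid patients who receive first trimester screening through the intervention or Tobacco Treatment as Usual (TTAU) clinic", and women who report use are eligible.
- **Table 1.** The first row, common to both arms, is headed "Baseline <20 weeks gestation". It contains the ACOG tobacco screen and gives its purpose as screening for eligibility.
- **Inclusion criteria (also in Aim 1).** The full list is "1. Pregnant and age 18-44; 2. Tobacco user (self-reported) 3. Can read and write in English; and 4. Medicaid subscriber". None of the four items limits gestation.

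Two further statements fix the timing of outcome and exposure. The Statistical Analysis Plan says: "The primary outcome is smoking cessation in the third trimester, defined as urine cotinine level of <100 ng/mL". Table 1 places the matching visit at "28-34 weeks gestation". For the intervention, the protocol says: "At least once monthly, at routinely scheduled prenatal visits or through telephone, the CTTS will provide cessation counseling".

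On adjustment, the Statistical Analysis Plan lists maternal age and "gestational age at enrollment) may be included as covariates if linked to outcomes in bivariate analysis". The sample-size paragraph after Box 2 commits to demographic covariates in the repeated measures mixed model, but it does not name gestational age at enrollment. The Statistical Analysis Plan reserves mixed models for continuous outcomes and GEE for dichotomous ones, so that commitment does not clearly reach the primary cessation outcome. The same paragraph acknowledges that, with only two clinics, the intervention effect cannot be fully separated from differences between the clinic populations.

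**The concern.** The primary sample is tied to gestation and not to time since enrollment. A woman who enters later therefore has less time with the tobacco treatment specialist before her cotinine is measured. A loosely stated entry window leaves the amount of intervention behind the primary result loosely stated too.

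The design makes this matter more. Each arm is one clinic, so if the two clinics differ in typical gestation at entry, for whatever reason, that difference is also a difference between arms. An entry rule that can be read in more than one way adds an avoidable source of such a difference. The only safeguard specific to it is a covariate that enters the model conditionally.

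The plan says the pilot's estimates will feed effect sizes for a larger study. An effect estimated under an unclear entry rule is hard to carry forward.

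**Working it through.** The plan states no figure for this point, so there is none to reproduce. The check has three parts.

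**1. Are the windows different rules for the same step?** Aim 1 attaches the ACOG questionnaire to first trimester screening and uses the answer for eligibility. Table 1 places the ACOG screen, with eligibility as its stated purpose, at a baseline before 20 weeks. The same instrument serves the same purpose under two time limits. The numbered criteria give no limit, and no text links the three.

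**2. Time from entry to the primary sample.**

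Inputs from the documents: primary window 28 to 34 weeks; Table 1 limit under 20 weeks (latest 19 weeks 6 days); counselling at least monthly.

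Assumptions: the first trimester ends at 13 weeks 6 days (the documents do not define it); earliest entry is 6 weeks; one session every 4 weeks.

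Formulas: shortest time = 28 − latest entry; longest time = 34 − earliest entry; sessions = weeks ÷ 4.

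- First trimester limit: shortest 28 − 13.86 = 14.1 weeks (3.5 sessions); longest 34 − 6 = 28 weeks (7 sessions).
- Under 20 weeks: shortest 28 − 19.86 = 8.1 weeks (2.0 sessions); longest 28 weeks (7 sessions).
- Difference in the shortest time: 14.1 − 8.1 = 6 weeks, and 6 ÷ 4 = 1.5 sessions.

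Session counts are minimums, because the protocol says at least monthly. The spread within one window is 28 − 14.1 = about 14 weeks under the first rule and 28 − 8.1 = about 20 weeks under the second. Choosing one window therefore leaves considerable variation in exposure, which is why the covariate matters as well as the wording.

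**3. How reliable is the bivariate screen?** The plan does not define its test. Assume a two-sided 0.05 test of correlation between entry gestation and outcome with n = 120, using the Fisher z approximation:

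power ≈ Φ(√(n − 3) × atanh(r) − 1.96), with √117 = 10.82.

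- r = 0.15: 10.82 × 0.1511 = 1.635; Φ(−0.325) = about 37%.
- r = 0.20: 10.82 × 0.2027 = 2.193; Φ(0.233) = about 59%.

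The two correlations are illustrations and not values from the documents. At either one, the screen would often leave out a covariate that is truly related to outcome. It also looks only at the link with outcome and ignores imbalance between arms, which is the other half of confounding.

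**The case against.** The case on the other side is substantial, and several parts of it stand.

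- **The windows could be sequential.** Aim 1 describes when routine care asks about tobacco, and baseline could follow at any time before 20 weeks. It is true that Aim 1 does not explicitly exclude a woman first seen later. But Table 1 puts the ACOG eligibility screen itself in the baseline row, so this reading is not secure, and the protocol does not state it.
- **The same text governs both clinics.** A reader might infer that the inconsistency will confound entry gestation with arm. The documents do not support that: nothing suggests the clinics would read the rule differently. Nor do they say that each clinic has its own recruiting staff. They say only who invites participants to complete assessments. Confounding is possible, not shown.
- **Exposure could appear to vary two-fold because of the inconsistency.** Entry at 8 weeks leaves 20-26 weeks before the sample and entry at 19 weeks leaves 9-15. Both entries lie inside the Table 1 window, so that spread would remain once the wording is harmonised. It does not measure this defect.
- **The criteria list alone would admit a woman at 30 weeks with no prior exposure.** That reading requires ignoring Table 1, which limits the eligibility visit to before 20 weeks. The fault is an omission from the list, not a plan to enroll in the third trimester.
- **Later entrants might be more persistent smokers.** This is plausible, but the documents give no figure for it, so it carries no weight here.
- **The root problem is one clinic per arm, and the protocol concedes it.** This stands. Clinic differences in booking gestation are aliased with arm under any entry rule. The general concession does not, however, justify leaving open a source of difference that can be closed cheaply.
- **Conditional covariate selection is a separate issue.** It would indeed apply with a perfectly consistent window. It belongs here because it is the plan's only specific protection against a difference in entry gestation.

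**Conclusion.** The point holds in limited form. The entry window is stated inconsistently and is missing from the formal criteria. The choice between Aim 1 and Table 1 moves the minimum time on intervention before the primary sample from about 14 to about 8 weeks, roughly 1.5 monthly sessions. This rests on a first trimester ending at 13 weeks 6 days and a session every 4 weeks.

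With one clinic per arm, a difference between clinics in entry gestation can bias the primary contrast. Neither its size nor its direction can be computed, because the documents give no entry-gestation distribution by clinic. The conditional covariate rule is weak protection at this sample size. This is worth correcting, but it does not by itself invalidate a pilot that already describes its clinic comparison as limited.

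**What to change.** 1. Reconcile Aim 1, Table 1 and the numbered inclusion criteria to one entry window, stated as an eligibility criterion. Under 20 weeks at baseline is the only numeric limit the documents give, so adopting it would change least. If first trimester entry is what the sponsor intends, Table 1 should say so.
2. In the Statistical Analysis Plan, make gestational age at enrollment a prespecified covariate in the primary third-trimester cessation model, whatever the bivariate result.
3. Report the distribution of gestational age at enrollment by clinic, so that readers can see whether the arms differ.

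The cost is a wording change, one degree of freedom, and the exclusion of any late-booking women whom the criteria list alone would admit. The covariate is one the plan already names. These steps narrow the possible clinic difference but leave the one-clinic-per-arm limitation, which only a design with several clinics per arm can resolve.

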## BOX 2. Typical Counseling Session with a CTTS for Pregnant Women

- Assessment of tobacco use and tobacco use history using an evidence-based tool
- Motivational and practical counseling based on assessment of readiness, including providing education on the maternal and fetal health impacts of smoking
- Provide strong advice to quit as soon as possible
- Exploration of the pros and cons of tobacco use/quitting (decisional balance) and triggers/cues to smoke, including partner smoking and potential engagement in treatment
- Collaboratively developing a tailored treatment plan, which may include but is not limited to incentives, and trigger management strategies, such as stress management or partner support
- Setting a quit date with close follow up
- Discussion relapse prevention strategies during the perinatal and postpartum periods

Our target sample size is 60 participants in each the intervention and control group, for a total of 120 pregnant participants for this pilot project. Additionally, 12 clinic staff and providers will provide quantitative and qualitative data for a mixed-method, multi-stakeholder process evaluation of intervention training and delivery. Due to our limitation of only two participating clinics, we acknowledge that it will not be possible to fully distinguish the effects of the intervention from differences between the two clinic populations. A future larger study of this intervention will include a true group randomized trial, with multiple clinics per treatment, so that the effect of nesting of patients within clinics within treatment will be estimable. In light of this limitation, we will use sample demographic characteristics as covariates in the repeated measures mixed modeling; we acknowledge that the group effects are still likely to be somewhat inflated in this analysis, given the expected artificially small errors due to correlations among patients who visit the same clinic and who may see the same provider. Although we will have limited power, the results from this pilot proof-of-concept study will provide preliminary data to support a highly competitive NIH Health Care Systems Research Pragmatic Trial application.

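### Enrolment follows clinic allocation, so motivated women may join the two arms at different rates, yet willingness to quit is not named as baseline data or pre-specified as a covariate.

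*Combined protocol and SAP*

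**What the plan says.** **Allocation.** The Study Design paragraph states: "Effectiveness questions will be explored using a two-armed cluster randomized controlled design". The text after Box 2 sets the number of clusters: "Due to our limitation of only two participating clinics". That means one clinic per arm.

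**Identification of women.** Aim 1 draws on "all pregnant Medicaid patients who receive first trimester screening through the intervention or Tobacco Treatment as Usual (TTAU) clinic", so the clinic carries its arm label before a woman is screened. Eligibility is open to every self-reported user: "All women who report tobacco use would be considered eligible to participate to receive ToPIC or TTAU".

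**Conflicting wording.** The two arm descriptions after Box 1 read as if individuals were allocated: "Eligible women randomized to the control group will be informed of the risks of tobacco use" and "Eligible women randomized to the intervention will receive TTAU plus ToPIC administered by the CTTS".

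**Willingness to quit.** Step 3 of Box 1 has the provider assess "the patient's willingness to attempt to quit smoking at the time". Because the ToPIC arm receives usual care plus the counselling, the 5A's are meant to reach both arms. The Table 1 baseline row lists urine cotinine, EACO and the ACOG tobacco use screen, and gives tobacco eligibility as their purpose.

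**Covariates.** The text after Box 2 offers demographic characteristics in response to the two-clinic limitation. The SAP adds: "Demographic and personal factors (e.g., maternal age, gestational age at enrollment) may be included as covariates". That inclusion is conditional on a bivariate link with outcome.

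**The concern.** In a cluster design that recruits after allocation, the enrolment step can unbalance the arms even when the two clinic populations are identical. The offers here differ. One clinic adds at least monthly counselling by a specialist; the other offers the care already given there, plus measurements. Gift cards are the same in both. A woman who wants help to quit may have more reason to join at the first clinic, and wanting to quit plausibly predicts quitting.

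The documents describe no concealment of arm at enrolment, no common invitation and no count of women who decline. Age or gestational age at entry would not be expected to stand in for motivation.

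This matters because the SAP puts its emphasis on average group differences, to supply effect sizes for a larger study. An inflated estimate would make that study too small.

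**Working it through.** **Step 1. Order of events.** Study Design and the text after Box 2 give clinic-level allocation with one clinic per arm. Aim 1 identifies women inside a labelled clinic. Together these put enrolment after allocation. The arm descriptions after Box 1 say that women are randomized, which does not fit. The protocol's own admission that treatment cannot be fully told apart from clinic makes sense only if clinics carry the arms.

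**Step 2. Where willingness appears.** It is in Box 1, step 3. It is not named in the Table 1 baseline row. Table 1 lists the 5A's separately, in the monthly row, which suggests that the baseline screen is the smoking-status question alone. It is not named in the SAP.

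**Step 3. The plan's reference effect.** The SAP illustrates its odds ratio of 2.3 with 50% versus 30%: (0.50/0.50)/(0.30/0.70) = 2.33, a difference of 20 points. This reproduces. The power figure attached to it is a separate matter and is not used here.

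**Step 4. Possible size of the bias.** From the documents: 60 women per arm and alpha 0.05, taken as two-sided (sidedness is not stated). Assumed, with no source in the documents: the share *w* of joiners willing to quit in each arm, and the cessation probabilities *q1* (willing) and *q0* (not willing), equal across arms so that there is no treatment effect.

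- Cessation in an arm: p = w·q1 + (1 − w)·q0
- Standard error: SE = √{[pT(1 − pT) + pC(1 − pC)]/60}
- Rejection rate: Φ(d/SE − 1.96) + Φ(−d/SE − 1.96), with d = pT − pC

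| Scenario | w, ToPIC v TTAU | q1 / q0 | pT v pC | d | OR | SE | Rejection |
|---|---|---|---|---|---|---|---|
| Mild | 60% v 50% | 40% / 20% | 32% v 30% | 2 points | 1.10 | 0.0844 | 5.6% |
| Middle | 60% v 40% | 45% / 15% | 33% v 27% | 6 points | 1.33 | 0.0835 | 11.1% |
| Strong | 70% v 40% | 50% / 10% | 38% v 26% | 12 points | 1.74 | 0.0845 | 29.5% |

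Strong case written out: pT = 0.7 × 0.50 + 0.3 × 0.10 = 0.38; pC = 0.4 × 0.50 + 0.6 × 0.10 = 0.26; OR = (0.38 × 0.74)/(0.26 × 0.62) = 1.74; d/SE = 0.12/0.0845 = 1.42. With a pooled variance under the null, rejection is 29.0%.

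**Step 5. Sensitivity.** Keeping 70% v 40% but weakening the gradient to 30% / 10% gives 24% v 18%, OR 1.44 and rejection 12.7%. With equal shares of willing women the bias is zero. These rates treat women as independent and so leave out the within-clinic correlation that the protocol mentions.

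**The case against.** Much of the opposing case stands, and it rules out several stronger readings.

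- **That every woman knows her arm when she joins.** A reader might infer this, but no passage states it. Consent pages are not part of the text under review, so their silence cannot count against the plan, and the individual-randomization wording pulls the other way. The supportable statement is that women can know.
- **That the willingness answer is discarded.** Aim 1 equates the ACOG questionnaire with the whole of Box 1, so the baseline screen could be read to include step 3. The SAP's personal factors are an open list. The supportable statement is that willingness is not named and not pre-specified.
- **That the imbalance could be neither seen nor adjusted for.** Baseline cotinine, EACO and the smoking-status categories, which separate women who have cut down from those who have not, are collected in both arms. They are imperfect but relevant markers.
- **That the authors overlooked confounding.** They admit that clinic and treatment cannot be fully separated, expect somewhat inflated group effects, and defer to a multi-clinic trial. Differential joining is a distinct mechanism, but it adds to a comparison already declared confounded.
- **That the false-positive rate is 30%.** No figure in the documents supports the size or the direction. The strong case needs a 30-point gap in willingness and a prognostic odds ratio of (0.50/0.50)/(0.10/0.90) = 9. The mild case is close to nominal.

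One objection bears on the remedy. Study Design describes the intervention as the 5A's delivered by a CTTS, and Table 1 places the 5A's within CTTS support. It is therefore not established that step 3 is asked before CTTS contact at the ToPIC clinic. If different staff ask it after different exposure, the answer may itself depend on arm, so its timing and source need to be written down.

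**Conclusion.** The point holds in a limited form. Enrolment follows allocation, no safeguard against differential joining is described, and the covariate plan does not pre-specify motivation although the 5A's ask about it in both arms. Across the three scenarios the spurious odds ratio runs from about 1.1 (5.6% rejection) to 1.7 (about 30%), against a planning value of 2.3. In the strong case the 12-point difference is more than half of the 20-point planning difference. That range rests entirely on assumed willingness shares and cessation rates, with no true effect and 60 independent women per arm. It shows what could happen and does not estimate what will.

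The point does not show that the pilot's result will be biased, or that the authors ignored confounding. It supports an inexpensive improvement, best made before enrolment, since baseline willingness and counts of decliners cannot be reliably recovered afterwards.

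**What to change.** 1. **Table 1, baseline row, both arms:** add willingness to quit (5A's step 3, yes/no), asked in the same way at both clinics by the usual-care provider and recorded before any CTTS contact.
2. **SAP:** enter that answer as a pre-specified covariate in the cessation GEE and the cigarettes-per-day mixed model, regardless of bivariate screening.
3. **Recruitment:** use one invitation script at both clinics, and state what women are told about their arm before they agree.
4. **Screening log:** report by clinic the number screening positive for tobacco, approached and declining. Keep counts only for decliners.
5. **Unit of randomization:** reconcile the individual-level wording after Box 1 with the cluster design in Study Design and the two-clinic text after Box 2.

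The cost is one field, one degree of freedom and a log, with no added visit or test. A yes/no answer captures motivation only roughly, so adjustment reduces this bias without removing it, and no covariate can separate clinic from treatment with one clinic per arm.
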